10. APPENDICES

10.1 IMMUNE-RELATED ADVERSE EVENTS OF SPECIAL INTEREST

Table 10.1: 1 Immune-related adverse events of special interest

This table defines immune-related AEs that must be reported as AESIs.

Immune-related adverse events of special interest
Pneumonitis (reported as an AESI if \geq Grade 2) 
• Acute interstitial pneumonitis• Interstitial lung disease• Pneumonitis
Colitis (reported as an AESI if \geq Grade 2 or any grade resulting in dose modification or use of systemic steroids to treat the AE) 
• Intestinal obstruction• Colitis• Colitis microscopic• Enterocolitis• Enterocolitis haemorrhagic• Gastrointestinal perforation• Necrotizing colitis• Diarrhea
Endocrine (reported as an AESI if \geq Grade 3 or \geq Grade 2 and resulting in dose modification or use of systemic steroids to treat the AE) 
• Adrenal insufficiency• Hyperthyroidism• Hypophysitis• Hypopituitarism• Hypothyroidism• Thyroid disorder• Thyroiditis• Hyperglycaemia, if \geq Grade 3 and associated with ketosis or metabolic acidosis
Endocrine (reported as an AESI) 
• Type 1 diabetes mellitus (if new onset)

Immune-related adverse events of special interest
Hematologic (reported as an AESI if \geq Grade 3 or any grade resulting in dose modification or use of systemic steroids to treat the AE)

• Autoimmune haemolytic anaemia• Aplastic anaemia• Thrombotic thrombocytopenic purpura• Idiopathic (or immune) thrombocytopenia purpura• Disseminated intravascular coagulation• Haemolytic-uraemic syndrome• Any Grade 4 anaemia regardless of underlying mechanism
Hepatic (reported as an AESI if \geq Grade 2, or any grade resulting in dose modification or use of systemic steroids to treat the AE)

• Hepatitis• Autoimmune hepatitis• Transaminase elevations (ALT and/or AST)
Infusion Reactions (reported as an AESI for any grade)

• Allergic reaction• Anaphylaxis• Cytokine release syndrome• Serum sickness• Infusion reactions• Infusion-like reactions
Neurologic (reported as an AESI for any grade)

• Autoimmune neuropathy• Guillain-Barre syndrome• Demyelinating polyneuropathy• Myasthenic syndrome
Ocular (report as an AESI if \geq Grade 2 or any grade resulting in dose modification or use of systemic steroids to treat the AE)

• Uveitis• Iritis

Immune-related adverse events of special interest	
Renal (reported as an AESI if \geq Grade 2)	

• Nephritis• Nephritis autoimmune• Renal failure• Renal failure acute• Creatinine elevations (report as an irAE if \geq Grade 3 or any grade resulting in dose modification or use of systemic steroids to treat the AE)	
Skin (reported as an AESI for any grade)	

• Dermatitis exfoliative• Erythema multiforme• Stevens-Johnson syndrome• Toxic epidermal necrolysis	
Skin (reported as an AESI if \geq Grade 3)	

• Pruritus• Rash• Rash generalized• Rash maculopapular• Any rash considered clinically significant in the physician's judgment	
Other (reported as an AESI for any grade)	

• Myocarditis• Pancreatitis• Pericarditis• Any other Grade 3 event that is considered immune-related by the physician	

10.2

MANAGEMENT OF IMMUNE-RELATED ADVERSE EVENTS

Management of immune-related event toxicities associated with anti-PD-1 mAbs are presented below. BI 754091 should be permanently discontinued for Grade 3-4 pneumonitis, Grade 3-4 adrenal insufficiency, Grade 4 diabetes mellitus, any grade encephalitis, Grade 4 hypophysitis, Grade 4 rash, Grade 3-4 or recurrent colitis of any grade, any recurrent Grade 3-4 AE, transaminase >5 times ULN or total bilirubin >3 times ULN, inability to taper steroids to 10 mg or less prednisone or equivalent within 12 weeks, or persistent Grade 2-3 AEs that do not recover to Grade 1 or less within 12 weeks.

- **Pneumonitis:**

- For Grade 2 events, treat with systemic corticosteroids. When symptoms improve to Grade 1 or less, steroid taper should be started and continued over no less than 28 days.
- Add prophylactic antibiotics for opportunistic infections in the case of prolonged steroid administration.
- For Grade 3-4 events immediately treat with i.v. steroids. Administer additional anti-inflammatory measures, as needed.
- BI 754091 should be permanently discontinued for Grade 3-4 pneumonitis, inability to taper steroids to 10 mg or less prednisone or equivalent within 12 weeks, or persistent Grade 2 AEs that do not recover to Grade 1 or less within 12 weeks.

- **Diarrhoea/Colitis:**

Subjects should be carefully monitored for signs and symptoms of enterocolitis (such as diarrhoea, abdominal pain, blood or mucus in stool, with or without fever) and of bowel perforation (such as peritoneal signs and ileus).

- All subjects who experience diarrhoea/colitis should be advised to drink liberal quantities of clear fluids. If sufficient oral fluid intake is not feasible, fluid and electrolytes should be substituted via i.v. infusion. For Grade 2 or higher diarrhoea, consider GI consultation and endoscopy to confirm or rule out colitis.
- For Grade 2 diarrhoea/colitis that persists greater than 3 days, administer oral corticosteroids.
- For Grade 3 or 4 diarrhoea that persists >1 week, treat with i.v. steroids followed by high-dose oral steroids.
- For Grade 3 or 4 colitis, or recurrent colitis of any grade, permanently discontinue BI 754091 and immediately treat with i.v. steroids followed by high-dose oral steroids.
- When symptoms improve to Grade 1 or less, steroid taper should be started and continued over no less than 28 days.
- BI 754091 should be permanently discontinued for Grade 3-4 or recurrent colitis of any grade, inability to taper steroids to 10 mg or less prednisone or equivalent within 12 weeks, or persistent Grade 2-3 AEs that do not recover to Grade 1 or less within 12 weeks.

- **Type 1 diabetes mellitus (if new onset, including diabetic ketoacidosis) Grade 3, or \geq Grade 3 hyperglycaemia, if associated with ketosis (ketonuria) or metabolic acidosis**
 - For Type 1 diabetes mellitus Grade 3-4 or Grade 3-4 hyperglycaemia

Proprietary confidential information © 2023 Boehringer Ingelheim International GmbH or one or more of its affiliated companies

- Insulin replacement therapy is recommended for Type I diabetes mellitus and for Grade 3-4 hyperglycaemia associated with metabolic acidosis or ketonuria.
- Evaluate subjects with serum glucose and a metabolic panel, urine ketones, glycosylated haemoglobin, and C-peptide.
- BI 754091 should be permanently discontinued for Grade 4 diabetes mellitus, any recurrent Grade 3 AE or persistent Grade 2-3 AE that does not recover to Grade 1 or less within 12 weeks.
- Hypophysitis:
 - For Grade 2 events, treat with corticosteroids. When symptoms improve to Grade 1 or less, steroid taper should be started and continued over no less than 28 days. Replacement of appropriate hormones may be required as the steroid dose is tapered.
 - For Grade 3 events, treat with an initial dose of i.v. corticosteroids followed by oral corticosteroids. When symptoms improve to Grade 1 or less, steroid taper should be started and continued over no less than 28 days. Replacement of appropriate hormones may be required as the steroid dose is tapered.
 - For Grade 4 events, permanently discontinue BI 754091, and treat with an initial dose of i.v. corticosteroids followed by oral corticosteroids. When symptoms improve to Grade 1 or less, steroid taper should be started and continued over no less than 28 days. Replacement of appropriate hormones may be required as the steroid dose is tapered.
 - BI 754091 should be permanently discontinued for Grade 4 hypophysitis, any recurrent Grade 3 AE, inability to taper steroids to 10 mg or less prednisone or equivalent within 12 weeks, or persistent Grade 2-3 AEs that do not recover to Grade 1 or less within 12 weeks.
- Hyperthyroidism or Hypothyroidism:

Thyroid disorders can occur at any time during treatment. Monitor subjects for changes in thyroid function (at the start of treatment, periodically during treatment, and as indicated based on clinical evaluation) and for clinical signs and symptoms of thyroid disorders.

 - For Grade 2 hyperthyroidism events (and Grade 3-4 hypothyroidism):
 - In hyperthyroidism, nonselective beta-blockers (e.g., propranolol) are suggested as initial therapy.
 - In hypothyroidism, thyroid hormone replacement therapy, with levothyroxine or liothyroinine, is indicated per standard of care.
 - For Grade 3-4 hyperthyroidism
 - Treat with an initial dose of i.v. corticosteroid followed by oral corticosteroids. When symptoms improve to Grade 1 or less, steroid taper should be started and continued over no less than 28 days. Replacement of appropriate hormones may be required as the steroid dose is tapered.
 - BI 754091 should be permanently discontinued for any recurrent Grade 3-4 AE, inability to taper steroids to 10 mg or less prednisone or equivalent within 12 weeks, or persistent Grade 2-3 AEs that do not recover to Grade 1 or less within 12 weeks.

- Hepatic:
 - For Grade 2 events, monitor liver function tests more frequently until returned to baseline values (consider weekly).
 - Treat with i.v. or oral corticosteroids
 - For Grade 3-4 events, treat with i.v. corticosteroids for 24 to 48 hours.
 - When symptoms improve to Grade 1 or less, a steroid taper should be started and continued over no less than 28 days.
 - BI 754091 should be permanently discontinued for any recurrent Grade 3-4 AE, transaminase >5 times ULN or total bilirubin >3 times ULN, inability to taper steroids to 10 mg or less prednisone or equivalent within 12 weeks, or persistent Grade 2-3 AEs that do not recover to Grade 1 or less within 12 weeks.
- Renal failure or nephritis:
 - For Grade 2 events, treat with corticosteroids.
 - For Grade 3-4 events, treat with systemic corticosteroids.
 - When symptoms improve to Grade 1 or less, steroid taper should be started and continued over no less than 28 days.
 - BI 754091 should be permanently discontinued for any recurrent Grade 3-4 AE, inability to taper steroids to 10 mg or less prednisone or equivalent within 12 weeks, or persistent Grade 2-3 AEs that do not recover to Grade 1 or less within 12 weeks.
- Adrenal insufficiency
 - BI 754091 should be permanently discontinued for Grade 3-4 adrenal insufficiency or persistent Grade 2 AEs that do not recover to Grade 1 or less within 12 weeks.
- Rash
 - BI 754091 should be permanently discontinued for Grade 4 rash, any recurrent Grade 3 AE or persistent Grade 2-3 AEs that do not recover to Grade 1 or less within 12 weeks.
- Encephalitis
 - BI 754091 should be permanently discontinued for any grade encephalitis.
- Infusion reactions:

Signs and symptoms usually develop during or shortly after drug infusion and generally resolve completely within 24 hours of completion of infusion.

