Main criteria for inclusion:	
Phase Ia Dose Escalation – adult patients with a confirmed diagnosis of advanced, unresectable, and/or metastatic solid tumours (any type) who have received all therapy known to confer clinical benefit (including anti-PD-1 therapies, if relevant and if the last dose of the prior anti-PD-1 was received more than 60 days prior to starting study drug), or for whom no therapy of proven efficacy exists, or who are not amenable to standard therapies
 
Phase Ib Dose Expansion – adult patients with a confirmed diagnosis of select advanced, unresectable, and/or metastatic solid tumours who are anti-PD-1/PD-L1 naïve but have failed conventional treatment (excluding anti-PD-1/PD-L1 treatment), or for whom no therapy of proven efficacy exists, or who are not amenable to standard therapies.
 
All patients must have measurable lesions according to Response Evaluation Criteria in Solid Tumours (RECIST) v1.1 and/or Immune-Related Response Evaluation Criteria in Solid Tumours (iRECIST).
 
Additional specific criteria for the individual expansion cohorts include:
 
- Cohort 4: Advanced and/or metastatic solid tumours including NSCLC, bladder cancer, melanoma, gastric cancer, ovarian cancer, TNBC, and RCC- Cohort 5: Patients with tumours that are TMB-high: any tumour with TMB-high status (>10 mutations/Mb), excluding those that are MSI-high (TMB and MSI status based on any validated test)- Cohort 6: Patients with squamous cell cervical, anal, and skin tumours that are refractory to standard therapies.- Cohort 7: Patients with recurrent HPV-positive, or HPV-negative, vaginal or VSCC	

Name of company:	Boehringer Ingelheim	
Name of finished product:	N.A.	
Name of active ingredient:	BI 754091	
Protocol date: 22 Sep 2016	Trial number: 1381.1	Revision date: 07 March 2023
Test product:	BI 754091	
Dose:	Phase Ia Dose Escalation : starting dose is 80 mg (1 mg/kg for a 80-kg person) once every 3 weeks (q3w) Phase Ib Dose Expansion : the RP2D established in Phase Ia	
Mode of administration:	Intravenous infusion	
Duration of treatment:	BI 754091 will be given on Day 1 of 21-day cycles for up to 1 year, or until progressive disease (PD) or unacceptable toxicity in the absence of other withdrawal criteria. If the patient is benefiting clinically at 1 year, he/she may continue after a case by case review with the sponsor, but no longer than 31 August 2023.	

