4.2.2.1 Permitted concomitant medications

- If medically feasible, patients taking regular medication should be maintained on it throughout the trial.
- Pre-medication will not be required, but may be utilised following the first dose of BI 754091. This includes medications for the management of nausea, diarrhoea, and vomiting for which the patient must be treated according to institutional standards.
- Supportive care and other medications that are considered necessary for the patient's well-being may be given at the discretion of the Investigator.
- Blood transfusions are allowed at any time during the trial, except to meet inclusion criteria. There must be at least 4 weeks between a patient's last transfusion and the screening laboratory assessment. Exceptions to this will be considered by the sponsor on a case by case basis.
- Patients already receiving erythropoietin at the time of screening for the trial may continue it, provided they have been receiving it for more than one month at the time trial treatment is started. Prophylactic erythropoietin should not be started during the first 3 weeks of any cohort, but may be started thereafter.
- Granulocyte colony stimulating factors should not be used prophylactically during the first 3 weeks of any cohort. Thereafter, prophylactic colony stimulating factors may be used according to institutional standards.
- For symptom control, palliative radiotherapy is permitted for any lesion in the dose-escalation part of the trial, except during the first cycle as it could interfere with the DLT evaluation for MTD determination. Following the first cycle of the dose-expansion phase (Phase Ib), palliative radiotherapy is allowed only for non-target lesions, following discussion with the Medical Monitor, provided that the reason for radiotherapy does not reflect PD and does not interfere with response assessment. Palliative radiotherapy is not allowed during the first cycle. Lesions that have been exposed to radiotherapy are no longer evaluable, and may not be included in the assessment of the non-target lesions and the overall assessment. These lesions may also not be used anymore for a trial biopsy. Unless in emergency situations, the Medical Monitor should be contacted prior to the administration of palliative radiotherapy in the expansion phase.

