4.2.2.2 Prohibited concomitant medications

- No other investigational therapy or anticancer agent should be given to patients. If such agents are required for a patient, then the patient must first be withdrawn from the trial.
- Immunosuppressive medications including, but not limited to systemic corticosteroids at doses exceeding 10 mg/day of prednisone or equivalent, methotrexate, azathioprine, and tumour necrosis factor-alpha blockers are prohibited. Use of immunosuppressive medications for the management of investigational product-related AEs or in patients

with contrast allergies is acceptable, and does not necessarily warrant immediate treatment discontinuation. In addition, use of inhaled, topical, intranasal corticosteroids or local steroid injections (e.g., intra-articular injection) is permitted. Temporary uses of corticosteroids for concurrent illnesses (e.g., food allergies, CT scan contrast hypersensitivity) are acceptable upon discussion with the Medical Monitor.

- Live attenuated vaccines during the trial through 30 days after the last dose of investigational product are prohibited.
- Herbal preparations/medications are not allowed throughout the trial unless agreed to by the Principal Investigator. These herbal medications include, but are not limited to: St. John's wort, kava, ephedra (ma huang), gingko biloba, dehydroepiandrosterone (DHEA), yohimbe, saw palmetto, and ginseng. If instructed by the Principal Investigator, patients should stop using these herbal medications 7 days prior to first dose of BI 754091.

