5.3.6.5.2 Immune-related adverse events (irAE)

Immune-related AEs are AEs associated with immunotherapy treatments that appear to be associated with the immune therapy's mechanism of action. These adverse reactions, which can be severe, may involve the gastrointestinal, skin, liver, endocrine, respiratory, renal, or other organ systems. All immune-related events are to be reported as AEs. Some irAEs also need to be reported as AESIs as defined in Table 10.1: 1. If an Investigator determines a Grade 3 event (not on the list) to be immune related, the Investigator should also report that event as an AESI.

Recommendations for the management of irAEs are presented in Appendix 10.2.

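### Protocol Section 10.2 starts steroids later for Grade 3 or 4 diarrhoea (more than 1 week) than for Grade 2 diarrhoea (more than 3 days) when the event is not judged to be colitis

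*Protocol*

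**What the plan says.** The Diarrhoea/Colitis part of Protocol Section 10.2 sets three steroid triggers.

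- Grade 2: "For Grade 2 diarrhoea/colitis that persists greater than 3 days, administer oral corticosteroids". This line covers plain diarrhoea as well as colitis.
- Grade 3 or 4 diarrhoea: "For Grade 3 or 4 diarrhoea that persists >1 week, treat with i.v. steroids followed by high-dose oral steroids". Colitis is not named here.
- Colitis at the higher grades or recurring: "For Grade 3 or 4 colitis, or recurrent colitis of any grade, permanently discontinue BI 754091 and immediately treat with i.v. steroids".

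The same part treats diarrhoea as a possible sign of bowel inflammation: "Subjects should be carefully monitored for signs and symptoms of enterocolitis (such as diarrhoea, abdominal pain, blood or mucus in stool". From Grade 2 upwards, gastrointestinal consultation and endoscopy are to be considered, with no deadline.

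Section 5.3.6.5.2 describes the status of this material: "Recommendations for the management of irAEs are presented in Appendix 10.2". Section 4.2.2.1 lets supportive care be used at the investigator's discretion, and Section 4.2.2.2 exempts immunosuppressants given for product-related adverse events from the general prohibition.

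**The concern.** One would expect the wait before steroids to shorten, or at least not lengthen, as the grade rises. For diarrhoea without a colitis finding it lengthens, from more than 3 days to more than 1 week, and the longer wait also covers Grade 4. The protocol gives no reason for this.

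A site that follows the written triggers would therefore start steroids later in the sicker patient. Section 2.3 of the protocol says that gastrointestinal immune-related events include diarrhoea and, less often, colitis, and that rare fatal colitis has been reported with this class. The late trigger thus falls on the more common presentation, and it applies until someone judges that colitis is present. The judgement that would move the patient to immediate treatment rests on a work-up that is only suggested.

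**Working it through.** The protocol states no figure to reproduce, and no power or error-rate formula applies. The check sets the written triggers side by side and counts days.

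**Inputs (all from Protocol Section 10.2, Diarrhoea/Colitis)**

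| Event | Written wait | Steroid regimen |
|---|---|---|
| Grade 2 diarrhoea or colitis | more than 3 days | oral |
| Grade 3 or 4 diarrhoea, not judged colitis | more than 1 week (7 days) | i.v., then high-dose oral |
| Grade 3 or 4 colitis, or recurrent colitis | none | i.v., then high-dose oral |

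**Count from onset.** The protocol does not say when the count starts. Assume that onset is Day 1.

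- Grade 2 trigger: met from Day 3 + 1 = Day 4.
- Grade 3 or 4 trigger: met from Day 7 + 1 = Day 8.
- Gap: 8 − 4 = 4 days, so Days 4, 5, 6 and 7 are affected.

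**Count from the day the higher grade is reached.** If Grade 3 is reached on Day k, the trigger is met from Day k + 7. The comparison is Day 4, when the same event would have been treated had it stayed at Grade 2.

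| Grade 3 reached on | Trigger met from | Later than Day 4 by |
|---|---|---|
| Day 1 | Day 8 | 4 days |
| Day 2 | Day 9 | 5 days |
| Day 3 | Day 10 | 6 days |

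Later values of k are not relevant: an event still at Grade 2 on Day 4 has already met the Grade 2 trigger.

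**Is there an earlier trigger elsewhere?** None was found in the current text. The permissions in Sections 4.2.2.1 and 4.2.2.2 allow earlier steroids but set no time. The Grade 2 oral-steroid line does not extend to Grade 3 or 4.

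**Is the pattern shared by other events in Section 10.2?** No. Grade 3–4 pneumonitis is treated with i.v. steroids at once. The steroid instructions for hypophysitis, Grade 3–4 hyperthyroidism, hepatic events and renal events carry no waiting period.

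**The case against.** The case against has several parts.

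- **The section is advisory.** It is presented as recommendations, and supportive medication "may be given at the discretion of the Investigator". Section 4.2.2.1 also refers to institutional standards for managing diarrhoea, and Section 8 leaves standard care with the treating physician. This stands in that no site is barred from treating earlier. But the institutional-standards wording sits in a bullet on pre-medication, and none of these places sets a steroid start. Permission to act sooner is not a trigger.
- **The affected group is narrow.** It is limited to Grade 3 or 4 diarrhoea thought to be immune-related but not judged to be colitis. That is correct, and it limits the weight of the point.
- **The regimens differ.** The 1-week line could be read as the point for moving to i.v. treatment, with oral steroids possible before then. The Grade 3–4 regimen is indeed the stronger one, so only the start time is inverted. However, no earlier oral start is written for these grades.
- **A wait allows colitis to be ruled out before high-dose steroids.** The same work-up is suggested from Grade 2, where the wait is only 3 days.
- **Other rules discourage delay.** Immune-related diarrhoea of Grade 2 or higher is an event of special interest (Table 10.1: 1) reportable within 24 hours. In Cycle 1, the irAE exception to the DLT definition requires a Grade 3 event to resolve on immunosuppression within 2 weeks (Section 4.1.5). Both reduce the risk of a passive wait, but neither says when to start steroids.
- **The 5- and 6-day figures assume that the count restarts at Grade 3.** They do. The text neither supports nor excludes a restart, so they are conditional; the 4-day gap does not need a restart.
- **Little treatment time remains.** Treatment under this protocol ends by 31 August 2023. The benefit is limited for that reason, though Version 8.0 is dated 07 March 2023 and leaves just under six months of possible dosing. SAP Section 7.8.1 also notes that immune-mediated events can begin more than 30 days after treatment.

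**Conclusion.** The concern holds. As written, Section 10.2 gives Grade 3 or 4 diarrhoea not judged to be colitis a later steroid start than Grade 2 diarrhoea. The gap is 4 days counted from onset, or 5 to 6 days for an event that worsens on Day 2 or Day 3 if the count runs from reaching the higher grade. Where the count starts is an assumption. The documents do not say how many patients would be affected.

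Grade 3–4 colitis is unaffected, and investigators may treat earlier. No effect on DLT counts, the MTD or any analysis follows. It is a patient-safety inconsistency in management guidance: modest in reach, but worth correcting because the correction is so small.

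**What to change.** In the Diarrhoea/Colitis part of Section 10.2, replace the 1-week trigger for Grade 3 or 4 diarrhoea with one no later than the Grade 2 trigger: after more than 3 days at the latest, or immediately, as for Grade 3–4 colitis. The clinical team should choose within that limit.

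The cost is one changed trigger, plus somewhat earlier steroid use in patients whose Grade 3 or 4 diarrhoea would have settled without it.
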